## **10.2. Statistical Analyses**

## **10.3. Demographic and Baseline Characteristics**

Demographics and baseline characteristics will be summarized using descriptive statistics for continuous variables, and frequencies and percentages for categorical variables.

## **10.4. Efficacy Analyses**

Efficacy will be evaluated for patients treated at the optimal dose level from the first 4 dose levels during Phase I together with those entered in the Phase II dose expansion portion of the study, and at any additional dose levels (if found to be tolerable and patients are recruited into the expansion cohort). The data from the two dose levels will be evaluated separately, and no formal statistical comparisons will be made between the two dose levels.

The efficacy endpoints are overall response rate (primary endpoint), time-to-progression, progression-free survival, and overall survival.

### **10.4.1. Primary Efficacy Endpoint(s)**

The overall response rate (CR, VGPR, or PR) will be presented along with 95% confidence intervals calculated using both asymptotic normal approximation and exact binomial methods.

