## 5. STUDY DESIGN

This is an open-label, non-randomized Phase I/II study of patients with relapsed or refractory multiple myeloma.

The Phase I study will determine the MTD of the combination of carfilzomib and panobinostat. The Phase I portion will follow a standard dose escalation design, beginning with dose level 1 (see Table 2). Patients will be assessed for dose-limiting toxicity (DLT) at each visit during Cycle 1 prior to receiving treatment. Dose modifications will not be permitted during Cycle 1 unless a patient experiences a DLT (see Section 5.2.2.). Treatment cycles will be administered at 28-day intervals. Panobinostat will be administered orally three times weekly during weeks 1 and 3 of each cycle (Days 1, 3, 5, 15, 17, 19). Carfilzomib will be administered intravenously on Days 1, 2, 8, 9, 15, and 16 of each cycle. During Cycle 1, the carfilzomib dose will be escalated after the Day 2 dose, if well tolerated.

A maximum of four dose levels were evaluated. No DLTs were seen during the Phase I portion.

In the Phase II portion of this study, patients with relapsed/refractory multiple myeloma will receive treatment with the dose level 4 panobinostat and carfilzomib combination. Patients will be reevaluated for response to treatment after each cycle (4 weeks). Patients with objective response or stable disease will continue treatment, with subsequent reevaluations every 4 weeks, until disease progression or unacceptable toxicity occurs.

[figure not shown]
A parallel Phase I study will occur to evaluate a minimum of 3 patients and a maximum of 6 patients following a standard dose escalation design at additional dose levels of the combination of carfilzomib and panobinostat (see Table 3).

If additional dose levels are found to be tolerable, then additional patients will be recruited into an expansion cohort which will be open at all sites - a maximum total of 36 patients (including the ones recruited into the parallel Phase I study) will be treated at this dose level. Sites will be notified about the expansion cohort and patients will enter in the dose level confirmed in their enrollment confirmation from SCRI Innovations.

Up to 80 eligible patients will be treated in the Phase I/II study. The treatment schema for the study is shown in Figure 2.

Figure 2

Treatment Schema

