### **5.3. Phase II**

If a dose level in the parallel Phase I study is found to be tolerable, then additional patients will be recruited into an expansion cohort of 30 patients for Phase II for a total of 60 Phase II patients (including 30 patients for dose level 4).. A maximum of up to 80 total patients may be enrolled in this study (including patients from the dose escalation Phase I studies).

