## 10. STATISTICAL CONSIDERATIONS AND DETERMINATION OF SAMPLE SIZE

### 10.1. Determination of Sample Size

MM 27 is a Phase I/Phase II study of carfilzomib in combination with panobinostat in the treatment of relapsed/refractory multiple myeloma. The total number of patients expected to be accrued is up to 80.

The Phase I efficacy objective is to establish the optimal dose of carfilzomib with panobinostat that can be administered to patients with relapsed/refractory multiple myeloma. In this part of the trial, the optimal dose combination to be administered will be determined as described in Section 5.2. Since 3-6 patients will be treated in each cohort, the maximum number of patients treated in this phase will be 24.

The Phase II efficacy objective is to evaluate the overall response in patients with relapsed/refractory multiple myeloma treated at the optimal dose level in the first 4 dose levels established during the Phase I portion. In addition, the overall response in patients at any additional dose levels will be evaluated. The response rates in the two dose levels will be evaluated separately. When used in the treatment of patients with relapsed/refractory multiple myeloma, the historical carfilzomib overall response rate is approximately 18%. It is hypothesized that the overall response rate for the treatment regimen of carfilzomib plus panobinostat is greater than that for patients treated with carfilzomib alone. A sample size of 27 achieves 80% power to detect an increase in the overall response rate to 36% (representing a 100% relative improvement) based on a one-sided test of proportion at an alpha level of 0.10. The sample size will be increased by 10% to account for potential non-evaluable patients and adjusted relative to the actual number of patients in the Phase I portion who are treated at the optimal dose level.

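### Section 10.4.1 does not carry the one-sided 0.10 test against 18% into the primary analysis, and one of its two 95% intervals falls short of 95% coverage

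*Combined protocol and SAP*

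**What the plan says.** The sample size rationale is in Section 10.1 and is repeated in the synopsis under Statistical Method. It takes 18% as the historical response rate on carfilzomib and states the hypothesis that the combination does better. It then says "A sample size of 27 achieves 80% power to detect an increase in the overall response rate to 36" per cent, "based on a one-sided test of proportion at an alpha level of 0.10". It adds "The sample size will be increased by 10% to account for potential non-evaluable patients", with a further adjustment for the Phase I patients treated at the optimal dose level.

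Section 10.4 analyses the optimal level from the first four using patients treated "during Phase I together with those entered in the Phase II dose expansion portion of the study". Any additional expanded level is analysed as well: "The data from the two dose levels will be evaluated separately", with no formal comparison between levels.

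Section 10.4.1 defines response as CR, VGPR or PR and says the rate "will be presented along with 95% confidence intervals calculated using both asymptotic normal approximation and exact binomial methods". That is the whole primary analysis. Section 10.2, Statistical Analyses, is a heading with no text under it.

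**The concern.** A reader who follows Section 10.4.1 alone would produce a rate and two intervals and would never run the test for which the trial was sized. Three things follow.

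- Nothing links the 95% intervals to the planned one-sided 10% test, and the two can point different ways on the same data.
- Two intervals are named and neither is said to govern. One of them does not deliver its stated 95%.
- The term used in 10.1 does not say whether the test is exact or approximate. For some numbers of patients that choice moves the success count by one responder.

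In an open-label, single-arm study these choices should be fixed in the analysis section before the responses are counted.

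**Working it through.** **Inputs.** Null 0.18, alternative 0.36, one-sided alpha 0.10, n = 27 (Section 10.1). Section 5.3 plans an expansion cohort of 30 "for a total of 60 Phase II patients (including 30 patients for dose level 4". Section 5 caps an additional level at 36. Assumption: the asymptotic normal interval is the Wald interval, p̂ ± 1.96 × √(p̂(1 − p̂)/n), because the plan does not define it further.

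**1. The plan's own figure.** The exact cut-off is the smallest r with P(X ≥ r | n, 0.18) ≤ 0.10, and power is P(X ≥ r | n, 0.36). At n = 27, P(X ≥ 7) = 0.200 and P(X ≥ 8) = 0.098, so r = 8, with power 0.812. The smallest n that reaches 80% exact power is 27, so the sample size reproduces. With the 10% allowance, 27 × 1.10 = 29.7, which rounds to 30.

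**2. Coverage of the two intervals.** Coverage is the sum of the binomial probabilities of every count whose interval contains the true rate.

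| n | Wald, true 18% | Exact, true 18% | Wald, true 36% | Exact, true 36% |
|---|---|---|---|---|
| 27 | 87.3% | 98.0% | 93.0% | 97.4% |
| 30 | 91.4% | 96.8% | 93.7% | 96.5% |
| 36 | 90.2% | 97.3% | 91.4% | 97.8% |

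Example at n = 27 and a true 18%: with 2 responders the Wald upper limit is 0.0741 + 1.96 × √(0.0741 × 0.9259/27) = 0.173, below 0.18. All counts of 0 to 2 therefore miss, with probability 11.2%. Counts of 10 or more miss on the other side, with probability 1.5%. Coverage is 100 − 11.2 − 1.5 = 87.3%. Averaged over true rates from 18% to 36%, Wald coverage is 92.2%, 92.7% and 93.0% at the three sizes.

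**3. The 95% intervals against the planned test, n = 27.**

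| Responders | Exact one-sided p | Planned test | Exact 95% | Wald 95% |
|---|---|---|---|---|
| 8 | 0.098 | met | 13.8–50.2% | 12.4–46.9% |
| 9 | 0.041 | met | 16.5–54.0% | 15.6–51.1% |
| 10 | 0.015 | met | 19.4–57.6% | 18.8–55.3% |

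At 8 and 9 responders the planned test succeeds while both intervals include 18%. The interval that matches the test is the one-sided 90% exact lower limit, the 0.10 quantile of a beta distribution with parameters x and n − x + 1. At 8/27 it is 18.1%, just above 18%.

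**4. Exact or z test.** The z test uses the null variance, no continuity correction and critical value 1.2816. Its true alpha is the exact binomial tail at its own cut-off.

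| n | Exact cut-off | Exact alpha | Exact power | z cut-off | z true alpha |
|---|---|---|---|---|---|
| 27 | 8 | 0.098 | 0.812 | 8 | 0.098 |
| 28 | 9 | 0.051 | 0.729 | 8 | 0.116 |
| 29 | 9 | 0.063 | 0.771 | 8 | 0.136 |
| 30 | 9 | 0.076 | 0.808 | 9 | 0.076 |
| 31 | 9 | 0.091 | 0.840 | 9 | 0.091 |
| 32 | 10 | 0.049 | 0.769 | 9 | 0.107 |
| 33 | 10 | 0.060 | 0.805 | 9 | 0.125 |
| 34 | 10 | 0.072 | 0.836 | 9 | 0.144 |
| 35 | 10 | 0.085 | 0.863 | 10 | 0.085 |
| 36 | 10 | 0.099 | 0.887 | 10 | 0.099 |

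The two tests differ at 28, 29, 32, 33 and 34. They agree at 27, 30 and 36, the sizes that the documents print.

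**The case against.** The test is in the plan. Sections 10.1 and 10.4.1 belong to one statistical chapter, 10.1 gives the null, direction, alpha and alternative, and 10.4 rules out only a comparison between dose levels. This stands: what is missing is the link, not the hypothesis. A reader might infer that the trial has no test at all, and the documents do not support that.

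A reader might also infer that a 95% lower limit above 18% is the success rule. That would need 10 of 27 responders and cut power to 0.528. No section gives the intervals that role, so this is a reason to label them and not a loss of power in the plan as written.

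A third tempting reading is that the choice between exact and z test is a live problem at many plausible sizes. That depends on an assumed number analysed. Section 5 reports "No DLTs were seen during the Phase I portion", and the escalation rule then enters 3 patients at a level. Adding 3 to 30 Phase II patients gives 33, where the tests differ. But Section 10.1 adjusts the sample size for Phase I patients at the optimal level, which may mean that they count toward the 30. The z test is also a weak candidate: its sample size formula gives 24.8, hence 25 and not 27. An arcsine formula does give 27, so the exact test is likely but not proven.

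On the intervals, the exact one is already specified, and the Wald misses at a true 18% fall mainly on the upper side, so they do not favour efficacy claims. Coverage is also not short at every rate: at n = 30 and a true 30% it is 95.3%. These points limit the harm. They do not make the normal interval a 95% interval at the plan's null or alternative rate for 27, 30 or 36 patients.

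**Conclusion.** The point holds as a gap in specification with one incorrect element. Section 10.4.1 does not connect to the powered test, and the normal-approximation interval misses its stated level by 3.6 to 7.7 percentage points at a true 18%, and by 1.3 to 3.6 points at a true 36%, for 27, 30 and 36 patients. The 95% intervals disagree with the planned test at 8 and 9 of 27 responders. At a true 36% those two counts together have probability 0.812 − 0.528 = 0.284, so the mismatch is not remote.

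The sample size itself is correct. The coverage figures rest on reading the normal approximation as Wald. The exact-versus-z question matters only if the number analysed is 28, 29, 32, 33 or 34, where the z test's true alpha is 0.107 to 0.144. The documents do not fix that number. This should be corrected, but it does not undermine the design.

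**What to change.** Amend Section 10.4.1 as follows.

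- Name the exact one-sided binomial test against 18% at alpha 0.10 as the primary analysis, at the optimal level from the first four dose levels.
- Print the success counts by number analysed: 8 at n = 27, 9 at n = 28–31, 10 at n = 32–36.
- Report the matching one-sided 90% exact lower limit.
- Apply the same test to any additional expanded level as a separate, supporting analysis, and state that it is not adjusted for multiplicity. Section 10.1 evaluates such levels in addition to the main objective. Two independent tests at 0.10 would give up to 1 − 0.90² = 0.19 chance of at least one false success.
- Keep the exact 95% interval, labelled descriptive, and drop the normal-approximation interval.

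The cost is a short wording amendment through Section 13.1, which requires approval by both drug suppliers and the Principal Investigator and submission to the IRB. No patients or data are added. The one drawback to state openly is that exact power falls to 0.73, 0.77 and 0.77 if the number analysed is 28, 29 or 32.

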#### **10.4.2. Secondary Efficacy Endpoint(s)**

Time-to-progression (TTP), progression-free survival (PFS) and overall survival (OS) will be analyzed using Kaplan-Meier methods. Time-to-progression will be measured from the date of first protocol treatment until the date of tumor progression is documented (event), or date of last adequate tumor assessment (censored). Progression-free survival will be measured from the date of first protocol treatment until the date of tumor progression is documented or death occurs (event), or date of last adequate tumor assessment (censored). Overall survival will be measured as the interval from first study treatment until date of death (event), or date last known alive (censored). Median progression-free survival and median overall survival will be reported using the respective point estimate and 95% confidence intervals.

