## History of Amendments for MM 27 (continued)

Amd	Amd Date	Revision(s) Made	Refer to this Section in the Protocol
5	03 August 2015	Moved hydration and safety guidelines for carfilzomib from Section 6.4	
 
• Section 5.1.2
 

		Deleted duplicate concomitant medication information	
 
• Section 5.4
 

		Added hypertensive events to Table 8	
 
• Section 6.3
 

		Added management guidelines for carfilzomib-related events	
 
• Section 6.4
 

		Amended to refer to the most current carfilzomib Investigator's Brochure.	
 
• Section 8.2.5
 

		Updated precautions and risks for carfilzomib	
 
• Section 8.2.6
 

		Amended response criteria for Progressive Disease as follows: Increase of $\geq 25\%$ from the nadir in at least one of the following criteria:	
 
• Appendix C
 

		
 
• serum M-protein (absolute increase must be <math>\geq 0.5</math> g/dL <del>and absolute value must be <math>\geq 1</math> g/dL</del>)
 
	

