#### **7.4. Re-Staging – 4 Weeks (-7 to Day 1 window allowed)**

- Bone marrow biopsy/aspiration (including cytogenetics and FISH for the following chromosomal abnormalities: 1q amplification, 1p del, t(4;14), t(11;14), t(14,16) or 17p del) (REQUIRED ONLY TO DOCUMENT A CR)
- Serum free light chain
- Serum immunoglobulin G, A, M
- SPEP and immunofixation
- UPEP and immunofixation requiring a 24-hour urine sample collection

At any point in this treatment, patients suspected of PD will have response assessed again to confirm disease progression (i.e. 2 sets of response assessments at least 1

week apart). The outcomes will be reviewed by the study chair before the patient is removed from the study. After the second set of response assessments, if disease progression is confirmed, the date of the first set of response assessments should be recorded as the progression date.

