PDc Progressive Disease	
Increase of <math>\geq 25\%</math> from the nadir in at least one of the following criteria:
 
 
• serum M-protein (absolute increase must be <math>\geq 0.5</math> g/dL)
 
• urine M-protein (absolute increase must be <math>\geq 200</math> mg/24h)
 
• only in patients with non-measurable serum and urine M-protein levels: difference in involved and uninvolved FLC levels (absolute increase must be <math>>10</math> mg/dL)
 
• only in patients with non-measurable serum and urine M-protein levels and non-measurable disease by FLC levels, bone marrow plasma cell percentage (absolute % must be <math>\geq 10\%</math>)
 
 
OR
 
 
• definite development of new lytic bone lesions or increase from baseline in size of lytic bone lesion(s)
 
 
OR
 
 
• development of new soft tissue plasmacytoma(s) or definite increase from nadir in existing soft tissue plasmacytomas
 
 
OR
 
 
• development of hypercalcemia (corrected serum calcium <math>>11.5</math> mg/dL) for patients without hypercalcemia at baseline. In case of preexisting hypercalcemia at baseline, PD will only be assessed due to the hypercalcemia criterion in case the corrected serum calcium level was <math>\leq 11.5</math> mg/dL post-baseline and increased thereafter beyond 11.5 mg/dL.
 

Patients with relapsed refractory myeloma (adopted from the European Group for Blood and Marrow Transplantation [EBMT] criteria)	
MR Minimal Response	
 
• <math>\geq 25\%</math> but <math>\leq 49\%</math> reduction of serum M protein and reduction in 24-hour urine M-protein by 50-89%
 
 
AND
 
 
• If present at baseline, 25-49% reduction in the size of soft tissue plasmacytomas is also required
 
• No increase in size or number of lytic bone lesions (development of compression fracture does not exclude response)
 

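### Serum M-protein progression was redefined in August 2015, and TTP and PFS use recorded progression dates with no rule for dates set under the earlier definition

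*Combined protocol and SAP*

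**What the plan says.** Section 10.4.2 defines the time-to-progression event as follows: "Time-to-progression will be measured from the date of first protocol treatment until the date of tumor progression is documented (event". Progression-free survival runs "until the date of tumor progression is documented or death occurs (event". Patients without an event are censored at the last adequate tumor assessment.

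Section 7.4 says how the date arises. Suspected progression needs a second set of assessments at least one week later, the study chair reviews the outcome, and if progression is confirmed "the date of the first set of response assessments should be recorded as the progression date".

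Section 9 refers to Appendix C (headed Appendix 3 in the body) for the criteria. The current serum criterion is a rise of at least 25% from nadir in "serum M-protein (absolute increase must be" at least 0.5 g/dL). No minimum absolute value is required.

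The History of Amendments records under Amendment 5, 03 August 2015: "Amended response criteria for Progressive Disease as follows". The words struck out there are "and absolute value must be" at least 1 g/dL.

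Section 5 reports on the first dose levels in the past tense: "A maximum of four dose levels were evaluated. No DLTs were seen during the Phase I portion". The log shows dose level 5 in Amendment 3 (26 March 2013) and dose level 6 in Amendment 4 (24 October 2013). Section 10.4 evaluates the dose levels separately and plans no formal comparison.

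**The concern.** The log differs from the current Appendix C, as it should; that is not the problem. The log matters only because it shows that the definition of a serum M-protein event changed after treatment had begun. The gap is in the current analysis text, which takes the progression date as documented and makes no provision for dates documented under the stricter rule.

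Followed literally, a patient regrowing from a low nadir before the change has an event at 1.0 g/dL. A patient with the same course afterwards has one at nadir + 0.5 g/dL. Both enter the same curve, and the reported median then corresponds to neither definition. The error runs one way: patients assessed under the earlier rule have longer recorded TTP and PFS than the current definition would give them.

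**Working it through.** The plan states no event count, median or power for TTP or PFS, so there is no figure of its own to reproduce here.

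**Inputs from the documents**
- Current serum rule: rise of at least 25% from nadir and at least 0.5 g/dL (Appendix C).
- Earlier rule: the same, plus an absolute value of at least 1 g/dL (Amendment 5 entry).
- Entry: serum M-protein of 0.5 g/dL is enough for measurable disease (Section 3.1).
- Restaging every 4 weeks on treatment (Sections 5.1.2 and 7.4).
- Single-agent carfilzomib median TTP: 5.1, 5.3 and 7.6 months (Section 1.3.1).

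**Step 1: where the rules differ**

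Current threshold = max(1.25 × nadir, nadir + 0.5). Earlier threshold = max(current threshold, 1.0). For nadirs below 2 g/dL the 0.5 g/dL increase governs, so the rules differ only if nadir + 0.5 < 1.0, that is, nadir < 0.5 g/dL.

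**Step 2: delay**

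Assume exponential regrowth with a doubling time of 1 to 3 months (not in the documents). Delay = log2(earlier ÷ current) × doubling time.

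| Nadir (g/dL) | Current | Earlier | Doublings | Delay (months) |
|---|---|---|---|---|
| 0 | 0.5 | 1.0 | 1.00 | 1.0–3.0 |
| 0.1 | 0.6 | 1.0 | 0.74 | 0.7–2.2 |
| 0.2 | 0.7 | 1.0 | 0.51 | 0.5–1.5 |
| 0.3 | 0.8 | 1.0 | 0.32 | 0.3–1.0 |
| 0.4 | 0.9 | 1.0 | 0.15 | 0.15–0.46 |
| 0.5 | 1.0 | 1.0 | 0 | 0 |

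A slower doubling time lengthens the delay in proportion; 6 months gives 4.4 months at nadir 0.1. With 4-weekly sampling, a value that passes both thresholds between two visits gives no difference.

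**Step 3: would both definitions occur?**

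The documents give no accrual or event dates. Amendments 3 and 4 precede Amendment 5 by 28.3 and 21.3 months. Assume uniform accrual over 6 to 18 months and exponential TTP with a median of 5.3 to 18 months. The share of progressions before 03 August 2015 is then 51–96% if accrual began in March 2013 and 36–91% if it began in October 2013. Every scenario has progressions on both sides of the change.

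**Step 4: effect on the median**

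Assume 10–30% of patients are affected, each delayed by 1 to 3 months, with true medians of 5.3 to 12 months. The simulated median moves by 0.1 to 1.0 month. For scale, the central 95% sampling range of a median from 33 uncensored patients (an assumed size) with a true median of 5.3 months is 3.1 to 8.4 months.

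**Step 5: difference between dose levels**

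For equal accrual length and median, the two start dates in Step 3 differ by 5 to 17 percentage points in the share before the amendment. Multiplied by 10–30% affected, this is 0.5% to 5.1% of patients, or about 0.15 (0.005 × 30) to 1.8 (0.051 × 36) people in a cohort of 30 to 36.

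**The case against.** The strongest reply is that the current documents are consistent: Section 9 names one Appendix C and Appendix C has one progression rule. An analyst could apply that rule to everyone's serial M-protein values without contradicting Section 10.4.2. That is possible, so mixing is not certain. But nothing requires it, and Section 7.4 creates a recorded progression date that an analyst would naturally use.

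Second, TTP and PFS are secondary and descriptive, with no test attached, and the likely shift is smaller than sampling error. This stands and limits the importance of the point. The shift is still in one direction, and a confidence interval does not allow for it.

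Third, 03 August 2015 is the amendment date. Section 13.1 requires IRB review, so the change may have taken effect later at individual sites. This also stands.

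A reader might go further and infer that any patient with a nadir below 0.5 g/dL is affected. That is too broad. Patients followed by urine or free light chain progress by routes not shown as changed, as do those with marrow, bone, plasmacytoma or calcium progression. Patients who never progress, or who progress after the change, are also untouched.

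A reader might also infer that the dose levels are biased against each other, with level 4 favored. The documents do not support this. They give no accrual dates, they call the level 5 and 6 study parallel, and they plan no formal comparison. The mix may differ between levels; no more can be said.

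**Conclusion.** The point holds in limited form. The serum M-protein progression rule was loosened during the trial, and Section 10.4.2 has no provision for dates recorded before that. The TTP and PFS estimates can, and probably will, combine two event definitions.

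The patients affected are those whose first progression criterion is serum M-protein, whose serum nadir is below 0.5 g/dL, and whose progression was assessed before the amendment took effect at their site. These are deep responders and patients who entered with little serum M-protein. Their number is unknown.

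Against quoted single-agent medians of 5.1, 5.3 and 7.6 months, the shift in the median is probably 1 month or less. That figure rests on the assumed share affected and the assumed delay of 1 to 3 months. The log shows no change to the CR, VGPR or PR definitions, so the primary response rate is unaffected; overall survival does not use progression. This is a cheap improvement and does not put the trial's main conclusion at risk.

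**What to change.** Put this in Section 10.4.2:

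> For all patients, whatever protocol version was in force, the biochemical progression date for TTP and PFS is derived from the recorded SPEP, UPEP and FLC values using the current Appendix C definition, taking the first of the two confirming assessments. Progression by bone marrow, bone lesion, plasmacytoma or hypercalcemia uses the recorded date. TTP and PFS on recorded, chair-reviewed dates are a sensitivity analysis.

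Add that the derived date is for analysis only and does not alter the recording and review procedure in Section 7.4.

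Deriving under the current rule is the feasible direction. Patients held to the stricter rule who stayed on treatment had 4-weekly values past the lower threshold, so the earlier crossing can usually be found. Deriving everyone under the earlier rule may not be possible, because Section 3.3 stops treatment at progression and later assessments are sparser.

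The cost is one paragraph and one derivation program on values already collected. TTP and PFS become slightly shorter for some earlier patients, and a derived date may precede the date treatment stopped.
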